 - Bone marrow dysplasia
 - Fecal incontinence
- Any other condition which, in the opinion of the Investigator, would make the subject unsuitable for trial participation

Study centers	3 sites in the United States
Start date/Duration	First patients are expected to be enrolled in January 2015. Accrual is estimated to last 1 year with up to 6 months of follow-up after the last patient has been entered.
Expected enrollment	63 patients
Rationale	The dose selected for this agent is (50 kBq (0.00135 mCi) (55kBq (.0015 after NIST update) administered every 4 weeks for 6 doses. This was selected based on prior studies, including the dose used in the randomized, phase III study that demonstrated a 31% reduction in the risk of death in comparison to placebo.
Objectives	
Primary
 
The primary objective of this study is to determine the effects of pain palliation with

Radium-223.

Secondary

The secondary objectives of this study are:

- To assess the impact of treatment on markers of bone turnover
- To assess the impact of treatment on PSA
- To assess the impact of treatment on time to radiographic progression
- To assess the impact of treatment on quantifiable imaging biomarkers assessing bone metabolism
- To assess the impact of treatment on tiredness
- To assess the toxicity of treatment
- To assess the impact of treatment on pain interference specifically evaluating its affect on general activity and sleep as measured by the BPI
- To assess the impact of treatment on time to pain progression
- To assess the impact of treatment on change in analgesic use

Study design This is an open, single arm phase II study.

The study will open in three sites in the U.S. Prostate Cancer Clinical Trials Consortium (PCCTC).

This is a two-phase design such that in the first phase, 27 patients will be accrued. If 6 or more patients achieve a pain response (defined as a 30% decline in the BPI worse pain item from baseline to week 8, with a confirmed reduction at week 12 without an escalation of the subjects pain regimen from Step 1 to Step 2 or Step 2 to Step 3 of the WHO analgesic ladder.), then an additional 36 patients will be enrolled. If fewer than 6 patients achieve a pain palliation response, the study will be terminated.

Treatment period: From first intravenous administration of study drug to 4 weeks after the last administration of study drug.

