3.3 Exclusion Criteria

Patients that meet any of the criteria listed below will not be eligible for study entry:

- Prior exposure to Radium-223
- Received an investigational therapy within the 4 weeks prior to registration, or is scheduled to receive one during the treatment period
- Received a new anti-cancer agent within 4 weeks prior to registration
- Received external beam radiotherapy within 4 weeks prior to registration
- Received systemic therapy with radionuclides (e.g. strontium-89, samarium-153, rhenium-186 or rhenium-188) for the treatment of bone metastases
- Treatment with cytotoxic chemotherapy within 4 weeks prior to registration
- Symptomatic nodal disease, i.e. scrotal, penile or leg edema.
- Visceral metastases (including cerebral metastases) from CRPC (>2 lung and/or liver metastases [size $\geq 2\text{cm}$]; Lymphadenopathy exceeding 6 cm in short-axis diameter or any

Radium-223

MSKCC

size pelvic lymphadenopathy if it is thought to be a contributor to concurrent hydronephrosis), as assessed by CT, MRI or chest X-ray within the 8 weeks prior to registration

PCCTC LOI: c13-124

IRB#: 14-098 A (5)

- Concurrent chemotherapy. Patients may be on other non-chemotherapy anti-cancer treatments, per FDA labeling of Radium-223, provided that these are not changed during the primary pain assessment period
- Major surgery within 30 days prior to registration
- Imminent spinal cord compression based on clinical findings and/or magnetic resonance imaging (MRI). Treatment should be completed for spinal cord compression.
- Patients with a, “currently active,” second malignancy other than non-melanoma skin cancers or non-invasive bladder cancers or other in-situ or non-invasive malignancies. Patients who have completed therapy for a prior malignancy and are free of disease for ≥ 3 years are eligible.
- Any other serious illness or medical condition, such as but not limited to:
 - Any infection \geq National Cancer Institute Common Terminology Criteria for Adverse Events (NCI-CTCAE) version 4.0 Grade 2
 - Cardiac failure New York Heart Association (NYHA) III or IV
 - Crohn’s disease or ulcerative colitis
 - Bone marrow dysplasia
 - Fecal incontinence
- Any other condition which, in the opinion of the Investigator, would make the subject unsuitable for trial participation

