In case of thrombocytopenia grade 3-4 the study drug administration should be delayed until recovery to CTCAE grade 2 (minimum $50 \times 10^9 / \text{L}$) or better.

In case of hemoglobin CTCAE grade 3-4, the value needs to recover to CTCAE grade 2 (minimum 8.0 g/dL) or better before next study drug administration. Blood transfusion is acceptable between study drug administrations.

Gastrointestinal events:

Diarrhea:

No prophylactic treatment for diarrhea is recommended. Antidiarrheals can be used when needed. A further dose of study medication should not be given before recovered to CTCAE grade 2 or baseline.

Nausea/Vomiting:

No prophylactic treatments for nausea or vomiting are recommended, but anti-emetic drugs can be used when needed. A further dose of study medication should not be given before recovered to CTCAE grade 2 or baseline.

Constipation:

Patients can continue laxative as concomitant medication, but start of prophylactic treatments before study drug injection are not recommended. Laxative can be used when needed. A further dose of study medication should not be given before recovered to CTCAE grade 2 or baseline.

Spinal Cord Compression

¹ Common Terminology Criteria for Adverse Events, Version 4.0 (CTC AE); Published May 28, 2009

Radium-223

MSKCC

PCCTC LOI: c13-124

IRB#: 14-098 A (5)

Patients, who experience spinal cord compression and require treatment with XRT in the treatment period prior to week 8, will be taken off-study and declared non-evaluable.

Surgical Intervention

If surgery is required, the patient should continue with study treatment, if this is considered safe in the treating Investigator's opinion. The surgeon needs to be notified that the patient has been given radioactive drug, and needs to follow the guidelines for radioactive protection.

Any Other Toxicity

If a patient experiences any non-hematological grade CTCAE grade 4 toxicity lasting > 7 days despite adequate treatment, further study drug administration must be discontinued.

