5.6.1 Withdrawal of subjects from study

Subjects **must be withdrawn from the trial** (treatment and procedures) for the following reasons:

- Subject withdraws consent from study treatment and study procedures. A subject must be removed from the trial at his/her own request or at the request of his/her legally acceptable representative. At any time during the trial and without giving reasons, a subject may decline to participate further. The subject will not suffer any disadvantage as a result.
- Subject is lost to follow-up.
- Death.

Subjects **may be** withdrawn from the study for the following reasons:

- The subject is non-compliant with study drug, trial procedures, or both; including the use of anti-cancer therapy not prescribed by the study protocol.
- If, in the investigator's opinion, continuation of the trial would be harmful to the subject's well-being.
- The development of a second cancer.
- Development of an intercurrent illness or situation which would, in the judgment of the investigator, significantly affect assessments of clinical status and trial endpoints.
- Deterioration of ECOG performance status to 4.
- Use of illicit drugs or other substances that may, in the opinion of the investigator, have a reasonable chance of contributing to toxicity or otherwise skewing trial result.

In all cases, the reason for withdrawal must be recorded in the CRF and in the subject's medical records.

Patients who are withdrawn from the protocol per reasons stated above will be replaced, unless they are evaluable by criteria specified in Section 10.2.1 Analysis Populations.

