10. STATISTICAL CONSIDERATIONS

10.1 Study Endpoints

10.1.1 *Analysis of the primary endpoint*

The primary objective of this phase II study is to determine the effect of Radium-223 on pain improvement for patients with symptomatic metastatic castration-resistant disease. The primary endpoint of the study is a 30% decline in the BPI worst pain item from baseline to week 8, with a confirmed reduction at week 12 without an escalation of the subject's pain regimen from Step 1 to Step 2 or Step 2 to Step 3 of the WHO analgesic ladder. The baseline BPI worst pain score average will be based on the worst pain scores completed by the patient in the 7 consecutive pretreatment days. A minimum of 4 days of pain scores must be completed by the patient in the 7

day window in order to calculate the average worst pain score. We define this event as a response and propose declaring the treatment effective if the probability of a response in the population exceeds 0.20.

A maximum of 63 patients will be entered onto the study. A two-stage design that differentiates between response rates of 0.20 and 0.35 will be used to assess treatment efficacy. In the first stage of the study 27 patients will be enrolled. If at most 5 patients respond, accrual will be terminated. If at least 6 patients respond, an additional 36 patients will be entered onto the study. At the conclusion of this second stage, if at least 17/63 patients respond, the treatment will be declared effective. The probability of declaring the treatment effective is 0.10 when the response rate in the population is 0.20 and increases to 0.90 when the response rate is 0.35.

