10.2 Analysis Populations

10.2.1 *Evaluable population*

Responders will be defined by a 30% decline in the BPI worst pain item from baseline to week 8, with a confirmed reduction at week 12 without an escalation of the subject's pain regimen from Step 1 to Step 2 or Step 2 to Step 3 of the WHO analgesic ladder.

Patients with progressive pain will be defined by time until a ≥ 2 point increase in the average "worst pain" item on the BPI over a 7 day period compared to baseline is seen and confirmed at least 2 weeks later.

Patients who are neither categorized as pain responders or are categorized as ones with progressive pain will be recorded as non-responders.

All patients who meet eligibility criteria and receive at least 1 dose of study medication will be included in the main analysis of the response rate, even if there are major protocol deviations (e.g., incorrect treatment schedule or drug administration). Each patient will be assigned to one of the above categories.

10.2.2 *Safety population*

All patients enrolled in the study will be included in the safety analysis population and considered evaluable for toxicity and safety from the time of their first dose. Demographic and baseline characteristics for the safety population will be summarized by number and percent for categorical data (e.g., sex, race/ethnicity) and by descriptive statistics for continuous data (e.g., weight, vital signs, EKG readings, disease status).

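### Section 5.5 labels some dosed patients non-evaluable, while Section 10.2.1 keeps every eligible dosed patient in the primary response analysis

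*Combined protocol and SAP*

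**What the plan says.** Section 5.5, under Spinal Cord Compression, provides that patients with this event who "require treatment with XRT in the treatment period prior to week 8, will be taken off-study and declared non-evaluable". The synopsis defines the period concerned: "Treatment period: From first intravenous administration of study drug to 4 weeks after the last administration of study drug". Anyone covered by the 5.5 rule has therefore received study drug.

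Section 10.2.1, headed as the evaluable population, says that patients who meet the eligibility criteria and "receive at least 1 dose of study medication will be included in the main analysis of the response rate", even where there are major deviations. It defines responders, patients with progressive pain, and non-responders (the remainder), and adds: "Each patient will be assigned to one of the above categories".

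Section 5.6.1 deals with replacement. Patients withdrawn for the reasons it lists "will be replaced, unless they are evaluable by criteria specified in Section 10.2.1 Analysis Populations". One listed reason is development of an "intercurrent illness or situation which would, in the judgment of the investigator, significantly affect assessments of clinical status and trial endpoints". Section 10.1.1 fixes the size of the trial: "A maximum of 63 patients will be entered onto the study".

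**The concern.** The same dosed patient is outside the primary denominator under 5.5 and inside it under 10.2.1. Section 10.2.1 has no cord-compression exception and does not refer to 5.5; 5.5 does not refer to 10.2.1. No text ranks one above the other.

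The exclusion rests on an event after dosing, and its direction is known. Response requires a 30% fall at week 8 that is confirmed at week 12. A patient taken off study before week 8 cannot document that, so 5.5 can remove only patients who would not count as responders. This also sits poorly with another rule in 5.5, which counts unequivocal clinical progression as treatment failure.

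Two things are at stake: the reported response rate and, if a site or analyst reads the 5.5 label as grounds for replacement, the type I error of a single-arm trial judged on counts out of 27 and 63.

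**Working it through.** **Inputs (Section 10.1.1).** Stage 1 has 27 patients and stops if 5 or fewer respond. Stage 2 adds 36, for a total of 63. The treatment is declared effective with at least 17 responders. The null rate is 0.20 and the target rate 0.35; the stated probabilities of success are 0.10 and 0.90.

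**Step 1: reproduce the design.** With X1 ~ Bin(27, p) and X2 ~ Bin(36, p),

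P(success) = Σ (x = 6 to 27) P(X1 = x) · P(X2 ≥ 17 − x).

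- p = 0.20: 0.0999 (stated 0.10)
- p = 0.35: 0.9019 (stated 0.90)

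The plan's figures reproduce with fixed denominators of 27 and 63.

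**Step 2: assumption on frequency.** The documents give no rate of cord compression needing radiotherapy before week 8. I take k = 1, 2 or 3 affected patients as an assumed range, none of them a responder, and read 0.20 as the rate among all dosed patients.

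**Step 3: patients dropped, not replaced.** The responder count does not change, so the rules of 6 and 17 give the same decision and type I error stays at 0.0999. Only the reported percentage moves. At the success boundary, against 17/63 = 27.0%:

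| k | reported rate |
|---|---|
| 1 | 17/62 = 27.4% |
| 2 | 17/61 = 27.9% |
| 3 | 17/60 = 28.3% |

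If 17/63 were read as a proportion to be reached, which no section does, 1 to 3 exclusions would still require 17 responders, since 16/60 = 26.7% falls short of 27.0%. With 4 exclusions, 16/59 = 27.1% would pass.

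**Step 4: patients dropped and replaced.** To obtain 63 retained patients, 63 + k are dosed. The affected share is q = k/(63 + k), and the response rate among retained patients is 0.20/(1 − q). Putting that rate into the Step 1 formula:

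| k | q | rate among retained | P(success) |
|---|---|---|---|
| 0 | 0 | 0.2000 | 0.0999 |
| 1 | 1/64 = 0.0156 | 0.2032 | 0.1116 |
| 2 | 2/65 = 0.0308 | 0.2063 | 0.1242 |
| 3 | 3/66 = 0.0455 | 0.2095 | 0.1375 |

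**Step 5: the other reading of the null.** If 0.20 is instead the rate among patients left after the 5.5 exclusion, drop-and-replace leaves type I error at 0.0999. Dropping 1, 2 or 3 stage 2 patients without replacement, with the cut-off kept at 17, lowers it to 0.090, 0.080 or 0.071, and lowers power from 0.902 to 0.892, 0.881 or 0.868.

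**The case against.** The strongest reply is that the statistical section already answers the question. Section 10.2.1 defines the analysis set, gives every eligible dosed patient a category, and is the section that 5.6.1 names as the test of evaluability. On that view the 5.5 wording is a stray label in a section on dosing and toxicity. This is how I would expect a careful analyst to proceed, but no text says that 10.2.1 overrides 5.5, and 5.5 could equally be defended as a specific exception to a general rule.

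The type I error result needs replacement, and three things stand against that: cord compression is not named in 5.6.1 and enters only through the general item on intercurrent illness; 5.6.1 bars replacement of anyone evaluable under 10.2.1; and k replacements would exceed the 63-patient maximum. This stands, and replacement is the less likely scenario. The inflation also depends on reading 0.20 as a rate among all dosed patients, which the plan does not spell out.

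The group is narrow as well. Entry already excludes "Imminent spinal cord compression based on clinical findings and/or magnetic resonance imaging (MRI"), and a shift from 27.0% to at most 28.3% is small beside an exact 95% interval of about 16.6% to 39.7% for 17/63. That is correct. It limits the size of the effect but does not remove the contradiction.

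**Conclusion.** The concern holds. The two sections disagree on whether an eligible, dosed patient belongs in the primary denominator, and following 5.5 can only move the reported response rate upward.

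Without replacement, the decision rule is unaffected and the bias at the success boundary is 0.4 to 1.3 percentage points (27.4 − 27.0 to 28.3 − 27.0). With replacement, type I error rises by about 0.012 to 0.038. Both ranges rest on an assumed 1 to 3 affected patients, and the second also on an all-dosed null of 0.20. The sample size calculation itself is correct. The expected effect is small, but in a single-arm trial judged on a responder count, who is counted should be settled before responses are known. It should be fixed.

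**What to change.** Reconcile 5.5 with 10.2.1. In 5.5, replace the closing words that declare the patient non-evaluable with: *and, if eligible and dosed, will remain in the primary analysis population under Section 10.2.1, will not be counted as a responder, and will not be replaced*. Whether such a patient is recorded as progressive pain or non-responder then follows from the definitions already in 10.2.1.

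Writing an exception into 10.2.1 would also make the sections agree, but it would build the one-sided exclusion into the primary analysis. The clause above keeps the protocol's own population and its stated operating characteristics.

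The clinical rule on taking these patients off study stays as it is, and no rule for other radiotherapy is added. The cost is one clause of wording and a reported rate that may be slightly less favourable.

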5.6 Removing Patients from the Protocol

Patients will receive a maximum of 6 doses of Radium-223 on study unless one of the following criteria applies:

- Patient decides to withdraw from the study
- Symptomatic disease progression at any time
- Objective clinical disease progression
- Intercurrent illness that prevents further administration of treatment
- Unacceptable adverse event(s) that may or may not be directly related to treatment but that, in the judgment of the treating physician, makes it dangerous for the patient to be retreated
- General or specific changes in the patient's condition that render the patient unacceptable for further treatment, in the judgment of the investigator

Because an excessive rate of withdrawals can render the study uninterpretable, unnecessary withdrawal of patients should be avoided. When a patient discontinues treatment early, the investigator should make every effort to contact the patient and to perform a final evaluation. The reason(s) for withdrawal should be recorded.

5.6.1 Withdrawal of subjects from study

Subjects **must be withdrawn from the trial** (treatment and procedures) for the following reasons:

- Subject withdraws consent from study treatment and study procedures. A subject must be removed from the trial at his/her own request or at the request of his/her legally acceptable representative. At any time during the trial and without giving reasons, a subject may decline to participate further. The subject will not suffer any disadvantage as a result.
- Subject is lost to follow-up.
- Death.

Subjects **may be** withdrawn from the study for the following reasons:

- The subject is non-compliant with study drug, trial procedures, or both; including the use of anti-cancer therapy not prescribed by the study protocol.
- If, in the investigator's opinion, continuation of the trial would be harmful to the subject's well-being.
- The development of a second cancer.
- Development of an intercurrent illness or situation which would, in the judgment of the investigator, significantly affect assessments of clinical status and trial endpoints.
- Deterioration of ECOG performance status to 4.
- Use of illicit drugs or other substances that may, in the opinion of the investigator, have a reasonable chance of contributing to toxicity or otherwise skewing trial result.

In all cases, the reason for withdrawal must be recorded in the CRF and in the subject's medical records.

Patients who are withdrawn from the protocol per reasons stated above will be replaced, unless they are evaluable by criteria specified in Section 10.2.1 Analysis Populations.

5.7 Concomitant Medications

Because of the potential for drug-drug interaction, the concurrent use of all other drugs, over-the-counter medications, or alternative therapies taken within 2 weeks prior to the start of the study must be documented on the case report form (CRF).

Patients receiving bisphosphonates or denosumab (RANK-L inhibitor) may continue on these agents as standard practice throughout the study.

Patients who enter the trial receiving prednisone or steroids must continue on the same dose they were receiving at the time of baseline assessment.

Permitted

- Pain Regimen Modification Guidelines:
 - An attempt to optimize a pain regimen should be made prior to subject enrollment. The investigator will optimize the subject's pain regimen under advisement/guidance of the 2.2014 NCCN Adult Cancer Pain guidelines. Opioid rotation, use of adjuvants, institution of a sustained release medication to minimize frequent prn dosing will be utilized depending on the severity of pain, degree of opioid tolerance and side effects under advisement/guidance of the NCCN guidelines. Use and optimization of short acting opioids followed, if needed, by adding an extended-release or long-acting formulation described in the protocol reflect NCCN guidelines. The patient will usually be allowed rescue doses of short-acting opioids of 10% to 20% of 24-h oral dose (mg) as needed as per the NCCN guidelines.
 - At the time of enrolment, the subjects pain regimen will be graded according to the WHO analgesia ladder:

Radium-223

MSKCC

PCCTC LOI: c13-124

IRB#: 14-098 A (5)

- Step 1- non-opioid analgesics
- Step 2- weak opioid (tramadol, codeine, hydrocodone)
- Step 3- strong opioid analgesic (morphine, oxycodone, fentanyl, oxymorphone, levorphanol, and methadone).
- NSAIDs, steroids and other adjuvant non-opioid analgesics can be included at each step of the analgesics ladder.
- Treatment with non-conventional therapies (e.g., herbs [with the exception of St. John's Wort], acupuncture) and vitamin/mineral supplements is acceptable provided that, in the opinion of the investigator, such treatment will not interfere with the trial endpoints.
- Subjects may receive standard of care for any underlying illness.
- In the event of neutropenia, anemia, or thrombocytopenia, subjects may receive appropriate supportive care (e.g., transfusion, biologic response modifiers such as G-CSF or GM-CSF, prophylactic antibiotics, antifungals and/or antivirals, hematopoietic growth factors).
- Blood transfusions and erythropoietin are allowed during the study period but not within 4 weeks prior to first dose of study drug.
- If surgery is required during study drug treatment, the surgeon needs to be notified that the patient has been treated with a radioactive product and adequate precautions for radioactive protection should be applied during the surgical procedure. The patient should continue with study treatment if considered safe in the treating Investigator's opinion.

Concomitant treatments other than chemotherapy for prostate cancer are permissible, provided that they are started before the patient's pain assessments, and are not changed during the pain assessments. These agents will be recorded in the CRFs. These treatments may include, but are not necessarily limited to: Luteinizing-Hormone-Releasing hormone (LHRH) analogs, surgery, flutamide, bicalutamide, nilutamide, estramustine, ketoconazole, corticosteroids, estrogens, abiraterone, and enzalutamide.

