^b Imaging assessments will be performed every 12 weeks \pm 1 week. Bone scan, FDG PET (FDG will be done in consenting patients and is considered optional), CT scan or MRI of the abdomen and pelvis and CT scan of the chest or Chest X-ray

^c Hematology: White blood cells count (WBC), red blood cell count (RBC), hemoglobin (HGB), hematocrit (HCT), platelet count (UNVPLT), neutrophils (NEUTP), lymphocytes (LYMP), monocytes (MONP), eosinophils (EOSP), basophils (BASOP)

^d Serum biochemistry: calcium (CA), albumin (ALB), total protein (TP), sodium (NA), potassium (K), chloride (CL), blood urea nitrogen (BUN), creatinine (CREAT), alkaline phosphatase (ALK), alanine transaminase (ALT), aspartate transaminase (AST), total bilirubin (TBILI), lactate

dehydrogenase (LDH), gamma-glutamyl transpeptidase (GGT), phosphate (PHOS), magnesium (MG), glucose (GLU), carbon dioxide (CO2)

- ^e Subjects should be followed up every 3 months following the safety follow-up visit for a total of 2 visits or until initiation of another therapy and be assessed for any potential long term toxicity as well as key efficacy parameters
 - ^f Subjects will indicate their daily pain score for 7 days during the 28 day screening period to establish that their average baseline pain score is ≥ 3 as measured for 4 of 7 days.
 - ^g During the follow-up period, subjects will answer questions on the BPI and BFI as well as enter information on their analgesic dairy for at least 4 of 7 days prior to their scheduled follow up visit
 - ^h Subjects will update their analgesic dairy daily during the run-in period and daily during the pain assessment periods throughout the trial
-

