During the Run-In Period, subjects will self-report pain and fatigue using a PRO instrument daily for 7 days and record analgesic medication information on a paper pain medication diary to establish that their BPI average baseline pain score is ≥ 3 as measured for a minimum of 4 of the 7 days (See Appendix I for instructions). This data will be used to confirm eligibility based on pain experience. Upon confirmation of eligibility, the subject's registration will be completed and the subject must start treatment within 5 days of registration.

Radium-223

MSKCC

PCCTC LOI: c13-124

IRB#: 14-098 A (5)

If run-in requirements are not met with respect to pain score, subjects may be eligible to rescreen at a later time.

5.2 Treatment/Intervention Period (Week 1, Day 1 to Week 25, Day 169 (treatment visits have a window of ± 3 days))

Unless otherwise specified, all visit procedures are to be performed prior to Radium-223 administration on the day of the visit. Radium -223 will be administered every 4 weeks for 6 doses at a dose of (50 kBq (0.00135 mCi) (55kBq (.0015 after NIST update) Because ALSYMPACA did not assess radiographic assessments during treatment, neither radiographic progression nor PSA progression should be used to discontinue treatment. However, patients are *permitted, per FDA labeling*, to be maintained on other anti-cancer therapies in addition to Radium-223 provided that these are not changed in the midst of pain assessments. Other-cancer therapies must be initiated 4 weeks prior to the run-in period. Patients with an increase in pain of 2 points on their BPI worst pain item compared to baseline and confirmed at least 2 weeks later will be considered to be treatment failures and will be taken off trial. In the absence of clinical progression, patients will continue to receive all six treatments, and will continue treatment until clinical progression, unacceptable toxicity, or any criteria in Section 5.6 Removing Patients from the Protocol. Patients will return to the clinic every 4 weeks for the following assessments:

- Physical exam
- ECOG performance status
- Vital signs [body temperature, blood pressure, pulse, respiratory rate, weight]
- ECG (as clinically indicated – not required at every visit)
- Lab tests [hematology, serum biochemistry, PSA, bone markers (to be done at the Wk 9 and Wk 13 visit)]
- Clinician reported adverse events and concomitant medications will be monitored continuously throughout the study

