8. CRITERIA FOR OUTCOME ASSESSMENT/THERAPEUTIC RESPONSE

8.1 Primary endpoint

The primary endpoint of the study is a 30% decline in the BPI worst pain item from baseline to week 8, with a confirmed reduction at week 12 without an escalation of the subject's pain regimen from Step 1 to Step 2 or Step 2 to Step 3 of the WHO analgesic ladder.

The baseline BPI worst pain score average will be based on the worst pain scores completed by the patient in the 7 consecutive pretreatment days. A minimum of 4 days of pain scores must be completed by the patient in the 7 day window in order to calculate the average worst pain score.

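### The no-escalation condition has no stated reference step, and the only scheduled WHO grading comes at enrolment, after the run-in that sets baseline pain, so an analgesic upgrade in between can count as response

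*Combined protocol and SAP*

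**What the plan says.** **Baseline pain.** Section 8.1 averages "the worst pain scores completed by the patient in the 7 consecutive pretreatment days", with at least 4 days completed. Section 5.1.1 places these days in a run-in from Day -7 to Day -1 (± 5 days) and says of them: "This data will be used to confirm eligibility based on pain experience". Registration is completed once eligibility is confirmed, and treatment starts within 5 days of registration. Footnote f to the schedule of assessments is looser: "Subjects will indicate their daily pain score for 7 days during the 28 day screening period".

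**Analgesic regimen.** Section 5.7 says: "An attempt to optimize a pain regimen should be made prior to subject enrollment". The pain criterion in Section 3.2 puts optimisation before study entry. Neither ties it to the start of the run-in. The only grading of the WHO step that the protocol schedules is in Section 5.7: "At the time of enrolment, the subjects pain regimen will be graded according to the WHO analgesia ladder".

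**Endpoint.** Sections 8.1, 10.1.1 and 10.2.1 require a 30% decline at week 8, confirmed at week 12, with no move from Step 1 to 2 or from Step 2 to 3. None of them says from which date or step the move is counted.

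**Other treatments.** Section 5.2 requires other anti-cancer therapies to have started 4 weeks before the run-in. Section 5.7 holds steroids at the dose in use at the baseline assessment. Analgesics have no equivalent rule, although footnote h has the analgesic diary filled in daily during the run-in.

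**The concern.** The no-escalation condition is there so that relief from stronger analgesia is not credited to radium-223. That works only if baseline pain and the reference step describe the same regimen. As written, they can describe different ones. A patient with poorly controlled pain in the run-in may move up a step before enrolment. His baseline score is then wholly or partly pre-upgrade, while his graded step is post-upgrade. The move is not an escalation, and the relief it brings counts toward the 30% decline. The trial has a single arm judged against a fixed rate of 0.20, so no control group would show the effect.

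**Working it through.** **1. Order of events under 5.1.1.** Run-in (baseline pain and diary), then eligibility confirmed on the run-in score, then registration completed, then first dose. A run-in average of at least 3 is an eligibility condition, so completed registration must follow the baseline score. If enrolment means completed registration, the WHO grade also follows it.

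**2. Length of the window.** The run-in lasts 7 days. The schedule of assessments puts Week 1 within 5 days after the run-in ends. From the first run-in day to first dose is therefore at most about 7 + 5 = 12 days. The part before enrolment is no longer than that.

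**3. The plan's own figures.** Inputs from Section 10.1.1:
- Null rate 0.20 and target rate 0.35.
- Interim rule: 27 patients, stopping at 5 or fewer responders.
- Final rule, after 36 more patients: "if at least 17/63 patients respond, the treatment will be declared effective"

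With X1 ~ Bin(27, p) and X2 ~ Bin(36, p):

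P(declare effective | p) = sum over x = 6 to 27 of P(X1 = x) × P(X2 ≥ max(0, 17 − x))

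This gives 0.0999 at p = 0.20 and 0.902 at p = 0.35, which match the stated 0.10 and 0.90.

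**4. Sensitivity to absorbed upgrades.** Two inputs are assumptions, because the documents give neither: f, the share of patients upgraded in the window, and r, the share of those who then meet the response definition, in place of 0.20. The observed null rate is

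p* = (1 − f) × 0.20 + f × r

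| f | r | p* | P(declare effective) |
|---|---|---|---|
| 0 | – | 0.200 | 0.100 |
| 2% | 40% | 0.98 × 0.20 + 0.02 × 0.40 = 0.204 | 0.115 |
| 2% | 60% | 0.98 × 0.20 + 0.02 × 0.60 = 0.208 | 0.131 |
| 5% | 40% | 0.95 × 0.20 + 0.05 × 0.40 = 0.210 | 0.140 |
| 5% | 60% | 0.95 × 0.20 + 0.05 × 0.60 = 0.220 | 0.187 |
| 10% | 40% | 0.90 × 0.20 + 0.10 × 0.40 = 0.220 | 0.187 |
| 10% | 60% | 0.90 × 0.20 + 0.10 × 0.60 = 0.240 | 0.304 |

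The rule is steep near 0.20: two extra percentage points of response nearly double the false-positive probability.

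**The case against.** **The sequence is not settled.** Enrolment is not defined. Sections 4.2 and 4.2.2 require registration before any treatment or study activity, which would put it ahead of the run-in. The pain criterion in 3.2 can be read as optimise first, then show residual pain of at least 3. If enrolment precedes the run-in, this route closes. This stands as a limit on the point, but 5.1.1 says plainly that registration is completed after the run-in, so the sections conflict.

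**The reference step is an inference.** No section says that the enrolment grade is the one the endpoint uses. The synopsis schema pairs daily pain reporting with the medication diary at baseline, so a reference taken from the run-in would also fit the text. This stands too. The enrolment grade is nevertheless the only one scheduled, and no rule turns the diary into a reference step.

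**The window is short and the hurdle is high.** The upgrade must fall within days, and the relief must reach 30% at week 8 and be confirmed at week 12. Step increases after first dose are still caught. This stands, and it argues for modest values of f and r.

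**Stronger readings to avoid.** A reader might infer from footnote f that the 7 baseline days may lie anywhere in the 28-day screening period, leaving weeks for a change. Section 5.1.1 and the 5-day start rule largely rule that out, so the footnote is loose wording to align. A reader might also infer that the plan does produce false responders. The text permits such upgrades but says nothing about how often they occur.

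**Conclusion.** The concern holds as a gap in the endpoint definition. No section names the reference step, the only grading follows the baseline pain score under 5.1.1, and no rule keeps the analgesic step stable from run-in to first dose. An upgrade in that window can therefore count as response. The conclusion rests on two readings: that enrolment follows the run-in, and that the enrolment grade is the endpoint's reference.

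The size is unknown. The range of about 0.11-0.30 against the stated 0.10 depends wholly on the assumed 2-10% upgraded and 40-60% responding, so it shows sensitivity and is not an estimate. The change is worth making because the correction is cheap and the endpoint is judged without a control arm.

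**What to change.** 1. In 5.7, 8.1 and 10.1.1, define the reference WHO step from the run-in analgesic diary for the same 7 days that give the baseline pain score. Count any rise above that step through week 12, including between run-in and first dose, as escalation for the endpoint.
2. For a patient whose step changes within the run-in week, pre-specify one consistent handling, for example a sensitivity analysis that counts him as a non-responder. Treating every rise after the first run-in day as escalation would penalise a patient whose baseline average is mostly post-change.
3. Report how many regimens changed between run-in and first dose.
4. Reconcile the order of optimisation, run-in, registration and enrolment across 3.2, 4.2, 5.1.1 and 5.7, and align footnote f with 5.1.1 and 8.1.

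**Cost:** a few sentences, using diary data already collected. The 63 patients and the 5/27 and 17/63 boundaries stay as they are. The response rate may fall slightly. This concerns only how the endpoint is scored; clinical management of analgesia is left to the investigators.
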